7.6.1 Antiemetic Medications

Dexamethasone and a 5-HT3 blocker (e.g., ondansetron or granisetron) may be administered to subjects as pre-medications unless contraindicated for the individual subject. Antiemetics will also be prescribed as clinically indicated during the study period.

7.6.2 Colony Stimulating Factors

Though unlikely to be needed, the use of granulocyte colony-stimulating factors is permitted to treat subjects with neutropenia or neutropenic fever but not to allow for study eligibility.

7.7 Dietary Restrictions

None.

7.8 Prohibited Medications

The following therapies are not permitted during a subject's participation in the study:

- Other anti-neoplastic therapy, including cytotoxics, targeted agents, endocrine therapy, or other antibodies, including Avastin® (bevacizumab) with any treatment intent. NOTE: Low-dose bevacizumab (Avastin®) (doses typically used to control radiation induced necrosis, see section 6.2) use is permitted
- Radiotherapy
- Any other investigational therapy

Should such therapies be administered if a subject is withdrawn from the study due to progressive disease, relevant disease related treatment data will continue to be collected until death or termination of data collection by the Sponsor or withdrawal of consent by the subject.

8 REPORTING AND DOCUMENTATION OF RESULTS

8.1 Evaluation of Efficacy

8.1.1 Overall Survival

The time from start of treatment to the date of death from any cause. For subjects who are not known to have died as of the data-inclusion cut-off date, OS time will be censored at the date of the last contact confirming the subject was alive.

8.1.2 Progression-free survival

The time from start of treatment to the date of confirmed objective progression or death from any cause, whichever occurs first. For subjects who are not known to have died or progressed as of the data-inclusion cut-off date, PFS time will be censored at the date of the last objective progression-free disease assessment prior to the date of any subsequent recurrent GB treatment.

PFS will be determined by RANO-based assessments, adopting the general approaches described for the modified RANO (mRANO) assessment with the response rubric of iRANO (for immunotherapy agents). Additional response assessments will incorporate the use of advanced imaging modalities (e.g. MRI perfusion / diffusion assessments) in the m/iRANO approach, to support differentiation of true vs. pseudo progression / response.

8.1.3 Objective Response Rate

Objective Response Rate (ORR) is the proportion of subjects who achieved a complete response (CR) or partial response (PR) out of all treated subjects.

According to the modified RANO criteria, a responder is defined by radiographic and clinical criteria (Ellingson *et al.*, 2017a). CR and PR together with Stable Disease (SD) and initial and confirmed Progressive Disease (PD) will be first assessed by radiographic changes in tumor size as determined by conventional MRI and further assessed by use of advanced imaging [e.g. diffusion weighted imaging, perfusion using dynamic susceptibility contrast and/or Tumor Response Assessment Maps (TRAMs), etc.] where available. In addition, deterioration of

neurologic function and increase in steroid use will be used to determine PD provided it is confirmed by advanced imaging and/or biopsy since extended duration of pseudo-progression is frequently observed following immunotherapies such as MDNA55 (Weber *et al.*, 2003a; 2003b; Okada *et al.*, 2015).

For the purpose of study endpoints, Objective Response (OR) status should be confirmed by repeat examination after at least 4 weeks. Patients who receive low-dose bevacizumab (Avastin®) treatment to control edema, a preliminary OR observed at least 4 weeks post-bevacizumab treatment will require a confirmatory OR after at least 4 additional weeks.

Subjects who remain on study following surgical resection / de-bulking with no histological evidence of recurrent tumor will have a best OR of SD following surgery and will continue to be followed by MRI as scheduled until new recurrence or confirmed PD to determine PFS.

Imaging assessment will be carried out using comprehensive imaging guidelines to help identify pseudo-progression where possible.

A blinded central review will be employed to provide independent assessment of response or progression following treatment with MDNA55 according to RANO-based criteria (Wen *et al.*, 2010; Ellingson *et al.*, 2017a) incorporating advanced imaging modalities. To rule out pseudo-progression, advanced imaging modalities and/or biopsy will be utilized.

8.1.4 Other Time-to-Event Endpoints

The time-to-event endpoints are defined in Table 8.

Table 8: Efficacy Endpoints

| Endpoint | Definition |
|--|---|
| Overall Survival (OS) at fixed times | OS at 6 (OS-6), 9 (OS-9) and 12 (OS-12) months will be estimated. |
| Progression- Free Survival (PFS) at fixed times | PFS at 6 (PFS-6), 9 (PFS-9) and 12 (PFS-12) months will be estimated. |
| Duration of response (DOR) | The time from first response until confirmed disease progression or death among those subjects achieving a complete response (CR) or partial response (PR) to treatment |
| Duration of clinical benefit (DOCB) | The time from first response or disease stabilization until confirmed disease progression or death among those subjects achieving a CR, PR, or stable disease (SD) |

The use of MRI is mandatory to determine tumor response and to assess when objective progressive disease has occurred (for use in estimating PFS, DOR, and DOCB).

8.2 Evaluation of Safety

Each subject receiving MDNA55 via CED will be evaluable for safety. Safety parameters include all laboratory tests and hematological abnormalities, physical findings, ECG, imaging parameters and AEs.

Each subject will be assessed periodically for the development of any toxicity as outlined in Section 7.5.

Definitions and reporting procedures for AEs provided in this protocol comply with current ICH E6 and other applicable international and local regulatory requirements. The Medical Monitor will promptly review all information relevant to the safety of MDNA55. The Investigator will carefully monitor each subject throughout the study for AEs and all AEs will be followed until adequately resolved. CTCAE 4.0 will be used to determine severity of AEs and SAEs.

8.2.1 Definitions

8.2.1.1 Adverse Event

An AE (also known as an adverse experience) is defined as any untoward medical occurrence

associated with the use of a drug in humans, whether or not considered drug related. More

specifically, an AE can be any unfavorable and unintended sign (e.g., an abnormal laboratory

finding), symptom, or disease temporally associated with the use of a drug, without any judgment

about causality. An AE can arise from any use of the drug (e.g., off-label use, use in combination

with another drug) and from any route of administration, formulation, or dose, including an

overdose.

Any condition present before the catheter placement, including pre-existing conditions and pre-

study AEs, will be considered medical history and will not be reported as a treatment-emergent

AE unless the condition worsens during or after catheter placement. Any worsening (i.e., any

clinically significant adverse change in frequency and/or intensity) of a preexisting condition,

which is temporally associated with the use of the Sponsor's product, is also an AE.

8.2.1.2 Adverse Reaction

An adverse reaction is defined as any AE caused by the use of a drug. Adverse reactions are a

subset of all suspected adverse reactions for which there is reason to conclude that the drug

caused the event.

8.2.1.3 Suspected

A suspected adverse reaction is defined as any AE for which there is a reasonable possibility that

the drug caused the AE. For the purposes of IND safety reporting, "reasonable possibility"

indicates that there is evidence to suggest a causal relationship between the drug and the AE. A

suspected adverse reaction implies a lesser degree of certainty about causality than an adverse

reaction.

8.2.1.4 Serious

An AE or suspected adverse reaction is considered serious if, in the view of either the Investigator

or Sponsor, it results in any of the following outcomes:

Death

Life-threatening AE

> an AE or suspected adverse reaction is considered life-threatening if, in the view of either the Investigator or Sponsor, its occurrence places the subject at immediate risk of death. It does not include an AE or suspected adverse reaction that, had it occurred in a more severe form, might have caused death.

Inpatient hospitalization or prolongation of existing hospitalization

applies if the reported AE requires at least a 24-hour in-patient hospitalization or, if in the opinion of the Investigator, prolongs an existing hospitalization. A hospitalization for an elective procedure or a routinely scheduled treatment is not an SAE by this criterion because a "procedure" or a "treatment" is not an untoward medical occurrence. An emergency room visit of less than 24 hours by itself does not constitute a SAE.

A persistent or significant incapacity or substantial disruption of the ability to conduct normal life function

Congenital anomaly/birth defect

 applies if a subject exposed to a medicinal (investigational) product gives birth to a child with congenital anomaly or birth defect.

Medical and scientific judgment should be exercised in determining seriousness in other situations, such as important medical events that may not be immediately life-threatening, result in death, or hospitalization, but may jeopardize the subject or may require intervention to prevent one of the other outcomes listed in the definition above. These events should be considered serious and subject to reporting procedures specified below in Section 8.2.2.4.

Examples of such events are intensive treatment in an emergency room or at home for allergic bronchospasm; blood dyscrasias or convulsions that do not result in hospitalization.

8.2.2 Evaluating and Recording of Adverse Events

At each visit, all AEs that are observed, elicited by the Investigator, or reported by the subject will be recorded in the appropriate section of the EDC System and evaluated by the Investigator and the Medical Monitor.

Minimum information required for each AE includes description of the event, duration (start and end dates), severity, assessment of seriousness, and causal relationship to study drug and delivery/infusion procedure.

If discernible at the time of completing the AE section in the EDC System, a specific disease or syndrome rather than individual associated signs and symptoms should be identified by the Investigator and recorded in the appropriate AE section in the EDC System. However, if an observed or reported sign, symptom, or clinically significant laboratory anomaly is not considered by the Investigator to be a component of a specific disease or syndrome, then it should be recorded as a separate AE in the appropriate AE section in the EDC System (clinically significant laboratory abnormalities are those that are identified as such by the Investigator and/or those that require intervention).

8.2.2.1 Relatedness of Adverse Events

The Investigator will assign attribution of the possible association of the event with use of the investigational drug and, separately, for the surgical/infusion procedure (i.e. AEs that occur during catheter placement prior to start of infusion of study treatment versus AEs with onset after start of infusion). Relationship will be determined for each as follows:

- Related: There is evidence to suggest a causal relationship between the drug and the AE, such as:
 - An event that is uncommon and known to be strongly associated with drug exposure (e.g., angioedema, hepatic injury, Stevens-Johnson Syndrome)
 - An event that is not commonly associated with drug exposure, but is otherwise uncommon in the population exposed to the drug (e.g., tendon rupture)
- Unrelated: Another cause of the AE is more plausible (e.g., due to underlying disease or
 occurs commonly in the study population), or a temporal sequence cannot be established
 with the onset of the AE and administration of the study treatment, or a causal relationship
 is considered biologically implausible.

In general, AEs that are worsening of baseline or pre-existing conditions are considered unrelated, unless there is reason to believe that the worsening was attributable to the investigational drug. Further, if death occurs due to progressive disease it is not considered attributable to MDNA55.

8.2.2.2 Severity of Adverse Events

The severity of AEs will be graded and recorded by the Investigator using the National Cancer Institute CTCAE version 4.0 guidelines. When specific AEs are not listed in the CTCAE 4.0 they

will be graded by the Investigator as *none*, *mild*, *moderate* or *severe* according to the following grades and definitions:

[figure not shown]
| Grade | Definition |
|----------|---|
| Grade 0 | No AE (or within normal limits) |
| Grade 1 | Mild; asymptomatic or mild symptoms; clinical or diagnostic observations only; intervention not indicated |
| Grade 2 | Moderate; minimal, local, or noninvasive intervention (e.g., packing, cautery) indicated; limiting age-appropriate instrumental activities of daily living (ADL) |
| Grade 3: | Severe or medically significant but not immediately life-threatening; hospitalization or prolongation of hospitalization indicated; disabling; limiting self-care ADL |
| Grade 4: | Life-threatening consequences; urgent intervention indicated |
| Grade 5: | Death related to AE |

8.2.2.3 Follow-up of Adverse Events

All AEs will be followed with appropriate medical management until resolved. Subjects withdrawn from study for unacceptable AEs will be followed until resolution or stabilization of the AE. For selected AE for which administration of the investigational drug was stopped, a re-challenge of the subject with the investigational drug may be conducted if considered both safe and ethical by the Investigator.

8.2.2.4 Serious Adverse Event Reporting

Within 24 hours of becoming aware of any SAE (regardless of its relationship to investigational product) that occurs during the course of the clinical study up until 12 months from start of infusion, the study personnel at the site must notify the pharmacovigilance vendor, ProPharma, within 24 hours of discovery using a written report (SAE Report Form) via Fax or Email as outlined in table below (the SAE Report Form must be submitted by the site within 24 hours even if it is incomplete). This ensures timely reporting of applicable reports to the applicable Health Authorities. The form must be signed by the Principal Investigator or designee, and if not available, the unsigned report should be faxed/emailed for initial processing and resubmitted after the Investigator's signature has been obtained.

will review the SAE documentation received for accuracy and completeness and follow-up with the Investigator to obtain missing information, if required. Upon receiving such notices, the Investigator must review and retain the notice and immediately submit a copy of this information to the IRB/IEC. The Investigator should also comply with IRB/IEC and / or any other specific procedures in their respective institution for reporting any other safety information. Where required, the Investigator must submit safety updates to the local Health Authorities.

All AEs and SAEs will be followed until the event has resolved or until the end of the study whichever occurs first. Follow-up SAE information should be aggressively collected and submitted as soon as new information becomes available by using the follow-up SAE Report Form and faxing/emailing this form to ProPharma. If the follow-up information changes the Investigator's and the Sponsor's assessment of seriousness or causality or relationship to the study drug, this change should be noted on the follow-up SAE Report Form. The initial and any follow-up SAE reports should be placed in the subject's file. For subjects that withdraw from the study, SAEs that occur within 30 days of the date of discontinuation, will be collected.

The Principal Investigator and Sponsor may stop the study at any time if the risk-benefit ratio is no longer favorable for the subject.

SAEs must also be reported on the AE page of the EDC System with corresponding terminology, onset/stop dates and assessment of severity, causality, subject outcome, treatment, and action taken.

If it is determined that the event meets expedited safety reporting criteria (serious, unexpected, and related to study drug expedited reporting to Health Authorities is required.

Serious Unexpected Serious Adverse Reaction (SUSAR) Reporting to Sites:

ProPharma will provide a SUSAR safety packet to all study Investigators at which point site must

submit the SUSAR safety packet to their IRB/IEC according to their local requirements.

Site must also observe the statutory reporting time frame for expedited reporting of all SUSARs

to FDA:

Fatal or life threatening SUSARs:

Not later than 7 calendar days after the sponsor has information that the case reported fulfils the

criteria for a fatal or life-threatening SUSAR, with any follow up information to be reported within

a further 8 calendar days.

All other SUSARs:

Not later than 15 calendar days after the sponsor has information that the case fulfilled the criteria

for a SUSAR.

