7.2 Safety Evaluation

Safety will be evaluated through AE monitoring, clinical evaluations (*i.e.*, vital signs, physical examinations, electrocardiogram [ECG]), laboratory tests (*i.e.*, hematology, serum chemistries, and urinalysis), antibody (serum anti-MDNA55 antibody and neutralizing antibody where applicable) assessments, and plasma drug levels on PK samples from the signing of informed consent until the last study visit (360 days post-CED infusion or termination).

Version: v.6.1

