- j Baseline conditions/symptoms will be collected from Screening until Day 0 before subject is anesthetized for catheter placement surgery; any baseline condition or symptom noted prior to catheter placement will be recorded in the Medical History

k

- I see Study Pharmacy Manual for infusate preparation and dispensing instructions
- m Following completion of infusion (only after the end of infusion MRI and at any time prior to subject's discharge from the hospital), the catheters can be removed and the incisions closed in accordance with institutional practice. Removal of catheters must be performed by a delegated neurosurgeon.
- n All concomitant medications will be collected on the Electronic Data capture (EDC) system from the date of informed consent through 30-day safety period. Thereafter, concomitant medications associated with treatment-related SAEs and detailed anti-tumor therapy will be collected. Corticosteroid use will be collected until Day 360 or early withdrawal.
- All AEs will be collected from catheter placement through the end of study visit and all AEs and SAEs will be followed until resolution, stabilization, data cut-off, or death
- Subjects who complete the Day 360 assessment without disease progression or discontinue early without disease progression will continue to be followed for disease status until progression. After progression (documented on study or during post-study follow-up), subjects will continue to be followed for survival, post-study treatment(s) for GB and imaging for GB, where possible, until death (or termination of data collection by the Sponsor or withdrawal of consent by the subject).
- q Physical exam and KPS assessments will be performed after completion of infusion when the subject is ambulatory prior to hospital discharge
- Vital signs monitoring (without weight parameter) will be performed according to institutional best practice throughout entire surgical workflow for catheter placement and CED infusion; study specific vital signs check points during the surgical workflow are prior to initiation of anesthesia, following placement of all catheters but prior to patient being loaded into MRI machine for the real-time infusion monitoring segment and approximately 1 hour post initiation of infusion; NOTE: Site will record any abnormal vitals observed at any time during surgical vital signs monitoring as unscheduled findings.

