- Collection of blood sample for PK analysis (baseline)

Concomitant medications and treatments will be recorded from 14 days before infusion (Day 0) until the Day 360 (or early termination) visit, and AEs will be recorded from the time of signing the informed consent document until the Day 360 (or early termination) visit.

In addition, a serum pregnancy test must be performed within 14 days before infusion (Day 0) for all female subjects of childbearing potential.

While the above assessments are being carried out, screening MRI will be subject to review by CED experts pertaining to evaluation of suitability of tumor for convection. The screening MRI will also be sent to an independent central assessment of objective radiologic tumor characteristics.

Subjects will be approved for enrollment by the Medical Monitor following comprehensive review all screening results.

Following approval of subject for enrollment, Investigator/site will be notified and preliminary pretreatment catheter trajectory planning using CT scan and screening MRI (registered with iPlan® Flow Infusion planning software) can ensue (see Section 6.3 for catheter placement guidelines).

NOTE: use of iPlan® Flow software is required for catheter trajectory planning.

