7.5.3.2 Follow up (for period of 12 months After Infusion)

Following completion of infusion, subjects will return on Days 30 (\pm 3), 60 (\pm 7), 90 (\pm 7) and 120 (\pm 7), and every 8 weeks (\pm 7) thereafter until Day 360 to undergo follow-up MRI. For sites that may use TRAMs, delayed contrast extravasation MRI can be performed on Days 30, 60, 90, 120 and 180 for calculation of TRAMs image map to be used for exploratory analyses of tissue response (calculation of TRAMs may be performed at the other follow up visits as or if requested by the Investigator).

At all of the above-named visits concomitant medications/therapies and AEs will be assessed by asking non-leading questions, and the following procedures will also be performed:

Physical and neurological examinations including KPS

- Vital signs (pulse, respiratory rate, weight and blood pressure)
- Hematology, serum chemistry, and coagulation (Section 7.2.1)
- Serum pregnancy test (female subjects; Day 30 and Day 180 visits only)
- Collection of blood samples for immunogenicity (Day 30, Day 120, Day 240 and Day 360 or early termination)

At any time-point during the follow-up period, should analyses on tumor tissue sample material occur at the discretion of the Investigator (e.g. biopsies to establish tissue response status), result should be recorded and material retained for biomarker analysis, where possible.

Other assessments will be performed at the Investigator's discretion and as necessary to follow up any AEs previously recorded.

The Day 360 visit will be equivalent to the early termination visit and will end the subject's safety reporting.

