7.5.5 Post-Study Follow-Up

Subjects who complete the Day 360 assessment without disease progression or discontinue early without disease progression will continue to be followed for disease status until progression where possible. After progression (on study or during post-study follow-up), subjects will continue to be followed (by access of available medical records or via periodic telephone contact to the subject/caregiver), where possible, for survival, post-study treatment(s) for GB and imaging for GB until death (or termination of data collection by the Sponsor or withdrawal of consent by the subject).

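### On the natural reading, a new non-fatal SAE starting more than 30 days after early withdrawal need not be collected, even if related to the drug or procedure

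*Protocol*

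**What the plan says.** Protocol 8.2.2.4 contains two windows. The general one covers any SAE, whatever its relationship to treatment, "that occurs during the course of the clinical study up until 12 months from start of infusion". The specific one applies to early leavers: "For subjects that withdraw from the study, SAEs that occur within 30 days of the date of discontinuation, will be collected". It makes no exception for events related to MDNA55 or to the procedure.

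Other sections set the end of safety recording:
- 7.5.3.2: "The Day 360 visit will be equivalent to the early termination visit and will end the subject's safety reporting".
- 7.5.1.2: "AEs will be recorded from the time of signing the informed consent document until the Day 360 (or early termination) visit".
- 7.2: safety evaluation runs to the last study visit, which is Day 360 or termination.
- Table 7, AE note: "All AEs will be collected from catheter placement through the end of study visit". SAP Table 2, note o, repeats this.

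Leaving the study does not end contact. Section 7.5.4 sends subjects withdrawn before Day 360 into post-study follow-up. Under 7.5.5 this is done through medical records or telephone, for disease status until progression and afterwards "where possible, for survival, post-study treatment(s) for GB and imaging for GB until death". AEs and SAEs are not in that list.

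**The concern.** Subjects normally receive one infusion, so the period at risk from the drug and the catheters starts at Day 0 for everyone. For early leavers, however, the SAE window is tied to the date of leaving, and leaving depends on outcome: 4.4 lists confirmed progression, an AE and the start of new GB treatment among the reasons.

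The protocol itself says that treatment effects can look like progression. Section 1.4.1 describes edema, mass effect and symptoms that cannot be told apart clinically from progressive disease, and 7.1.2 allows pseudo-progression to last more than 3 months. Subjects withdrawn for apparent progression could therefore include some with drug or procedure effects.

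What is at stake is completeness. Late non-fatal serious events related to treatment could be under-ascertained in the subjects who leave early, and a single-arm trial has no control group that might show it.

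**Working it through.** The plan states no figure on this point, so the check is a reading of the text and a day count.

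**1. Which window governs a withdrawn subject?** Suppose that the 12-month rule in 8.2.2.4 also covered subjects who withdraw. For withdrawal on day d, the 30-day sentence would then add something only if d + 30 > 360, that is, if d > 330. It would have a function only for withdrawals in the last month, and the rule would conflict with 7.5.3.2, which ends safety reporting at the early termination visit. If the 30-day sentence is the rule for withdrawn subjects, it has a clear function, and 7.2, 7.5.1.2, 7.5.3.2 and the Table 7 note all point the same way. That is the natural reading.

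**2. What is still caught after withdrawal plus 30 days?**
- Deaths, through survival follow-up (7.5.5, 8.1.1).
- Events already open: under the Table 7 note "all AEs and SAEs will be followed until resolution, stabilization, data cut-off, or death", and 8.2.2.3 follows AEs that led to withdrawal. Neither covers new onsets.
- Serious, unexpected events related to study drug, under the expedited rules in 8.2.2.4, but only once the sponsor learns of them.

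The remainder is new, non-fatal SAEs. These include related events that are expected and events related to the procedure. No section requires the site to look for them.

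**3. How long is the uncovered period?** Inputs: the 30-day window (8.2.2.4) and Day 360 as the end of safety reporting (7.5.3.2).

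Days outside the window = max(0, 360 − (d + 30)).
- d = 60: 360 − 90 = 270 days
- d = 120: 360 − 150 = 210 days
- d = 240: 360 − 270 = 90 days
- d = 330 or later: 0 days

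**The case against.** The best counter-argument is that the text does not exclude late SAEs. The reporting duty in 8.2.2.4 is triggered by awareness of any SAE and runs from infusion. Section 4.3 sets a study duration of 12 months for each subject. The 30-day sentence contains no word such as only, and 4.4 says that all treated subjects should be followed for safety. This stands to the extent that the protocol is not fully explicit. It does not remove the problem, because 4.4 gives no period or procedure and the sections that do give an end date point to early termination.

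A second argument is that the limit is a defensible choice. Exposure is normally one infusion of 24 to 48 hours, systemic exposure is not expected (7.2.3), and catheters are out before discharge. Section 1.4.1 strongly recommends keeping subjects for at least 120 days, which with the 30 days gives about 150 days of coverage where it is followed. MRIs after withdrawal are still collected if possible (Table 6). Under 8.2.2.1, events better explained by the disease are classed as unrelated, so few late events may count as related. All of this is fair and keeps the priority low.

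A reader might go further and infer that the trial loses a known share of its serious safety events. The documents do not support that. They name no specific late-onset toxicity and give no withdrawal rate. Any share of follow-up time would rest on an assumed rate and would count time at risk of all SAEs, whereas the change proposed here adds only related ones. Risk after a single infusion on Day 0 also need not be constant over the year.

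**Conclusion.** The point holds as a gap in the collection rule. On the natural reading, a new non-fatal SAE starting more than 30 days after early withdrawal need not be collected, even if related to MDNA55 or the catheter/infusion procedure. This applies to subjects who have not withdrawn consent, and who remain in contact only where possible.

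The size that the text supports is the day count above. It assumes only that 8.2.2.4 is read as it naturally reads and that Day 360 marks the end of the 12 months. It describes time outside the window, not missed events. Because no late toxicity is documented, this is a cheap improvement to consider. It touches no efficacy analysis, error rate or sample size.

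**What to change.** Keep the rule of any SAE to 12 months for subjects on study, and amend Protocol 8.2.2.4 for every treated subject who has not withdrawn consent:
- SAEs considered related to MDNA55 or to the catheter/infusion procedure are collected until 12 months from the start of infusion. After withdrawal this uses the existing 7.5.5 contact, where possible.
- All SAEs, regardless of relationship, are collected until at least 30 days after discontinuation.

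Then make the rest consistent:
- Align 7.2, 7.5.1.2, 7.5.3.2 and the Table 7 AE note, and SAP Table 2, note o.
- Add related SAEs to the post-study follow-up content in 4.3, 4.4, 7.1.1, 7.5.3 and 7.5.5.
- Flag events that start after next-line GB therapy. Section 8.2.2.1 already has drug and procedure attribution assigned separately. The start date of next-line therapy is less certain: 7.8 covers treatment after withdrawal for progressive disease, and 7.5.5 lists post-study treatment only after progression. Record the date for all withdrawn subjects if it is not already captured.

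Costs: under 10.3 this is a substantive amendment that needs investigator signature, IRB/IEC approval and FDA submission, so it is best combined with another amendment. Expect a few extra SAE forms. Attribution will be weaker after next-line therapy, and capture will stay incomplete because contact is only where possible.
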